#### MDD Subtype

Subjects will be dichotomized based on whether they have MDD with anxious distress or MDD without anxious distress (as determined by the SCID-CT) to evaluate whether there are differences in these subgroups (i.e., evaluating change from baseline to the end of Week 6 in the MADRS total score in subjects with and without anxious distress). Descriptive statistics of the change from baseline to the end of Week 6 in the MADRS total score will be presented by treatment group for these subgroups.

#### **Baseline RRS Score**

The RRS consists of 22 items which are rated on 4-point Likert scales ranging from "almost never" to "almost always". The total score is calculated as the sum of the 22 items.

Subjects will be dichotomized based on their baseline RRS score to evaluate whether there are differences in these subgroups (i.e., evaluating change from baseline to the end of Week 6 in the MADRS total score in subjects with RSS score  $\geq$ the median versus subjects with RRS score <median). Descriptive statistics of the change from baseline to the end of Week 6 in the MADRS total score will be presented by treatment group for these subgroups.

In addition, the correlation between baseline RRS score as a continuous variable and change from baseline to the end of Week 6 in the MADRS total score will be evaluated by means of a scatter plot and if appropriate, regression analysis.

## 5.3. Secondary Efficacy Endpoints

#### 5.3.1. Response of Depressive Symptoms

#### 5.3.1.1. Definition

A secondary efficacy endpoint is the proportion of responders on depressive symptoms scale at the end of Week 6, defined as  $a \ge 50\%$  improvement in MADRS total score from baseline to the end of Week 6. The calculation of the MADRS total score is described in Section 5.2.1. The percentage change from baseline for MADRS total score is calculated as 100\*(MADRS total score at Day X – Baseline MADRS total score)/(Baseline MADRS total score). Negative percent changes in MADRS total score indicate improvement (eg, percent change < -50% indicates improvement >50%).

A subject is defined a responder (yes=1) at a given time point if the percent reduction in MADRS total score is  $\geq$ 50%. Subjects who do not meet such criterion will be considered as non-responders and will be assigned a value of 0 (i.e., no). Observed case analysis, i.e., no imputation for subjects with missing values, will be explored.

#### 5.3.1.2. Utility Estimand

The secondary endpoint of proportion of responders on depressive symptoms scale at the end of Week 6 can also be considered a "utility estimand", as it considers efficacy and tolerability data together. It is defined by the following 4 components:

**Population:** subjects with MDD who have had an inadequate response to current antidepressant therapy with an SSRI/SNRI, as defined through appropriate inclusion/exclusion criteria to reflect the targeted patient population;

**Variable:** is binary (responder or non-responder), as defined in Section 5.3.1.1; subjects who do not have a MADRS total score at the end of Week 6 (eg, subjects who have early discontinuation of study drug) will be considered non-responders;

**Intervention Effect:** is not applicable as the intercurrent event (discontinuation of study drug) is captured in the variable definition;

Summary Measure: the difference in response proportions.

The analysis will be based on the full analysis set and the MADRS total scores collected during the double-blind phase.

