Vital signs	X		X	 		X		X		X		X
Clinical laboratory tests: hematology,			Λ				 					Λ
serum chemistry, and urinalysis	X		X			X		X ^s		X		
Lipid Panel ^h			X							X		
HbA1c ^h	X									X		

Phase	Screen	ning		Double-Blind								Follow-up ^a	
										End-of- Treatment/Early Withdrawal ^a	Telephone Contact	Follow-up visit	
Study Day	-28 to -3	-1	1 ^b	2	7	8 ^c	21	22	41	42	43	49-56	
Study Week	-4 to -1	-1	1	1	1	2	3	4	6	6	7	7-8	
Visit (window ± 2 days)	1	ı	2	-	-	3	-	4	-	5	-	6	
Visit Type ^d	Out-Patient		Overnight at the study site		Out-Patient								
Serum/Urine pregnancy test ^t	X ^t		X ^t					X^{t}		X^{t}		X^{t}	
C-SSRS	X		X			X		X		X		X	
ASEX			X							X			
PWC					•					X	X	X	
Concomitant medications	← Continuous ← ▶												
Adverse events	← Continuous ←												

Abbreviations:

ASEX=Arizona Sexual Experiences Scale, CGI-S=Clinical Global Impression-Severity, C-SSRS=Columbia Suicide Severity Rating Scale, DNA=deoxyribonucleic acid, ECG=electrocardiogram, FSH=follicle stimulating hormone, FT₄= free thyroxine, HbA1c=hemoglobin A1c, EQ-5D-5L=European Quality of Life (EuroQol) Group, 5-Dimension, 5-Level questionnaire, HAM-A=Hamilton Anxiety Rating Scale, ICF=Informed Consent Form, ISI=Insomnia Severity Index, MADRS=Montgomery-Asberg Depression Rating Scale, MGH-ATRQ=Massachusetts General Hospital-Antidepressant Treatment Response Questionnaire, PHQ-9=Patient Health Questionnaire 9-item, PGI-S=Patient Global Impression-Severity, PK=pharmacokinetic, PROMIS-SD=Patient Reported Outcome Measurement Information System-Sleep Disturbance, PROMIS-Fatigue=Patient Reported Outcome Measurement Information System-Sleep Disturbance, PROMIS-Fatigue=Patie

Footnotes:

- a. If a subject discontinues study treatment before the end of Week 6, end-of-treatment and follow-up assessments should be obtained.

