#### 2.5. Visit Windows

As subjects do not always adhere to the protocol visit schedule, the following rules are applied to assign actual visits to analysis visits. Listed below are the visit windows and the target days for each visit. The reference day is Study Day 1 (which is the first day the study drug was taken in the double-blind phase). If a subject has 2 or more actual visits in one visit window, the visit closest to the target day will be used as the protocol visit for that visit window. The other additional visit(s) will not be used in the summaries or analyses but they can be used for determination of clinically important end points. If 2 actual visits are equidistant from the target day within a visit window, the later visit is used.

All assignments will be made in chronological order. Once a visit date is assigned to a visit window, it will no longer be used for a later time point except for the end point (DB). Listed below (Table 1) are the visit windows and the target days for each visit defined in the protocol.

Assessments prior to Day 1 of the double-blind phase that are not considered a baseline assessment will be labeled as 'Screening'.

Parameter	Analysis Phase	Scheduled Visit Number	Time Interval (label on output)	Time Interval (Day)*	Target Time Point (Day/Time)
MADRS	Screening	1	Screening	< 1	-28 to -3
	DB	2	Baseline	≤1	1
		3	Day 8	2 to 15	8
		4	Day 22	16 to 32	22

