## 5.1.2. Data Handling Rules

As sensitivity analyses, the change in MADRS total score, MADRS-6 total score, HAM-A total score, and PHQ-9 total score will be analyzed using an analysis of covariance (ANCOVA) model, using last observation carried forward (LOCF) data. These analyses are further described in Sections 5.2.3.3, 5.3.4.2, and 5.3.8.2.

For the analyses of response of depressive symptoms based on MADRS total score (Section 5.3.1), remission of depressive symptoms based on MADRS total score (Section 5.3.2), response of anxiety symptoms based on HAM-A total score (Section 5.3.5), and response and remission of depressive symptoms based on PHQ-9 total score (Section 5.3.8.2), both observed case and imputed case where subjects with missing values will be imputed as non-responders/non-remitters will be presented.

For the graphical presentations of the cumulative response rates, defined as the percentage of subjects experiencing at least a given value of percent reduction from baseline to the end of Week 6 for MADRS total score (Section 5.3.1), HAM-A total score (Section 5.3.5), and PHQ-9 total score (Section 5.3.8.2), both observed and LOCF data will be presented. Since ISI is collected at only 1 postbaseline time point, the cumulative response curve for ISI (Section 5.3.3.2) will be presented using observed data.

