#### 5.3.1.3. Analysis Methods

The number and percentage of subjects who achieve a response will be summarized at each time point during the double-blind phase by treatment group. The point estimate and 2-sided 90% confidence interval will be provided for the relative response using a Mantel-Haenszel test controlling for region and baseline insomnia status (present/absent).

The cumulative response rate, defined as the percentage of subjects experiencing at least a given value of percent reduction from baseline to the end of Week 6 in MADRS total score, will be presented graphically, for both observed and LOCF data.

The cumulative distribution function of the time to sustained response will be estimated by the Kaplan-Meier method. Time to sustained response will be summarized (number of sustained responders, number of censored subjects, median, 25th and 75th percentile, if estimable) by treatment group. Sustained response is defined as the first occurrence of response on Day 8 or Day 22 that is maintained through the end of Week 6 assessment. Subjects are allowed one excursion (non-response) on a subsequent visit prior to Day 42, however the score must show at least 25% improvement. Subjects who discontinue early are not considered to have sustained response. A stratified log rank test (stratified for region and baseline insomnia status) will be used to test the hypothesis that there is no difference between the JNJ-42847922 dose groups and placebo in the probability of achieving sustained response.

A variation of definition for sustained response will be explored, for which no excursion is allowed. The analyses mentioned above will be repeated for this variation.

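### The Week 6 responder estimand says that stopping study drug is captured as non-response, but an early stopper with an exit MADRS on Day 33 or later can count as a responder

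*SAP*

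**What the plan says.** **The estimand.** SAP 5.3.1.2 presents the proportion of Week 6 responders as a utility estimand that weighs efficacy and tolerability together. It specifies no intervention effect, on the ground that this component "is not applicable as the intercurrent event (discontinuation of study drug) is captured in the variable definition". The variable assigns non-response to "subjects who do not have a MADRS total score at the end of Week 6 (eg, subjects who have early discontinuation of study drug"), so discontinuation appears only as an example of why a score might be absent.

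**The responder rule.** SAP 5.3.1.1: "A subject is defined a responder (yes=1) at a given time point if the percent reduction in MADRS" total score is at least 50%. It sets no condition on still taking study drug. SAP 5.1.2 plans an observed-case analysis and an "imputed case where subjects with missing values will be imputed as non-responders/non-remitters will be presented". That imputation is triggered by a missing value, not by stopping.

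**The visit windows.** SAP 2.5 says "the following rules are applied to assign actual visits to analysis visits". For MADRS, Table 1 gives Days 2-15 for Day 8, Days 16-32 for Day 22, and Day 33 to the end of the double-blind phase for Day 42. It makes no exception for early-withdrawal or off-drug visits.

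**The exit visit.** Footnote a to the protocol's Time and Events Schedule: "If a subject discontinues study treatment before the end of Week 6, end-of-treatment and follow-up assessments should be obtained". The schedule lists MADRS at the End-of-Treatment/Early Withdrawal visit.

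**The contrasting rule.** For time to sustained response, SAP 5.3.1.3 says: "Subjects who discontinue early are not considered to have sustained response".

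**The concern.** The estimand names stopping study drug as its intercurrent event and claims to handle it by counting it as failure. The working rule handles a missing score instead. The two agree only if every early stopper lacks a Week 6 score, and the exit visit combined with the wide Day 42 window means that some will have one.

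A late stopper, including one who stopped for tolerability, can then be counted as a success on an endpoint presented as penalising such stops. The same subject fails the sustained-response definition in the next subsection. The reported Week 6 response rates would not estimate the quantity that 5.3.1.2 describes.

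**Working it through.** **Step 1: is the exit score inside the double-blind phase?** SAP 2.2 ends that phase, for everything except adverse events, at the later of the last double-blind visit and the date of completion or early withdrawal. The exit MADRS therefore qualifies.

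**Step 2: which label does it get?** Applying the Table 1 windows to the day of the exit visit:

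- Exit on Day 31 or 32: labelled Day 22. With no later score, Week 6 is missing and the subject is a non-responder, as the estimand says.
- Exit on Day 33, 35, 39, 40 or 41: labelled Day 42. Week 6 is not missing, so the missing-score rule does not apply.

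The date of the visit decides, not the date of the last dose. A subject who stops before Day 33 but is seen on or after Day 33 is also affected. The worked example in SAP 5.2.3.3, in which an early final visit on Day 10 goes through the same windows, shows that exit visits are not set aside.

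**Step 3: one subject.** Study drug stopped on Day 34, exit visit on Day 35, MADRS down from 32 to 14. Percent change = 100 × (14 − 32)/32 = −56.25%. Under 5.3.1.1 this is a Week 6 responder; under 5.3.1.3 it is not a sustained responder.

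**Step 4: size.** The plan gives no figure to reproduce and no dropout timing, so this is an illustration. From SAP 1.4: 280 randomized, 25% dropout, hence 0.25 × 280 = 70 dropouts. The protocol's visit window is ±2 days, so a visit on Days 40-44 is on schedule. Only exits on Days 33-39 (7 days) are counted.

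Assumptions: every dropout gives an exit MADRS; the share exiting on Days 33-39 is 5%, 17.5% or 30%; and 20% or 50% of these meet the response criterion. The middle share is 7/40, from exits spread evenly over the 40 days 2-41.

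Affected subjects = 70 × share × proportion responding; percentage points = 100 × affected/280.

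| Share exiting Days 33-39 | Late exits | Affected at 20% | Affected at 50% |
|---|---|---|---|
| 5% | 3.5 | 0.7 (0.25 points) | 1.75 (0.625 points) |
| 17.5% | 12.25 | 2.45 (0.875 points) | 6.125 (2.19 points) |
| 30% | 21 | 4.2 (1.5 points) | 10.5 (3.75 points) |

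**The case against.** The best defence is that the intent is visible. SAP 5.3.1.2 itself cites early discontinuers as subjects without a Week 6 score, and protocol 10.1 equates the end of Week 6 with Day 42 and does not treat premature discontinuers as completers. On that view only a cross-reference is missing. The intent is indeed clear, but the SAP's only working definition of the Week 6 MADRS is the Day 42 window, and programming the text as written gives the opposite result for late stoppers.

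The size can also be challenged, and this largely stands. Protocol 10.2 includes loss to follow-up, withdrawal of consent and death among the withdrawal reasons, and such subjects may leave no exit score. In addition, simulating MCP-Mod power with 0.75 × 280 = 210 evaluable subjects (three arms, 2:1:1) gives an average of 86.4% over the candidate shapes, close to the stated 85% or so. The 25% thus appears to have been used as loss of Week 6 data. Read that way, those 70 subjects have no Week 6 score and are already non-responders. The table shows a possible order of size, not a forecast.

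A reader might infer more than the documents support:

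- **That the error enters Phase 3 dose selection.** Protocol 11.3 assigns that role to MCP-Mod applied to MMRM estimates of MADRS change. Response is secondary, with no multiplicity control.
- **That this is the only efficacy analysis penalising early stops.** Time to sustained response does so too, with a stratified log-rank test.
- **That the error favours the higher dose.** Nothing in the documents shows which arm will have more late stops. If they are balanced, the effect on the treatment comparison largely cancels.
- **That the Day 22 response table and remission carry the same contradiction.** They use the same windows, but no utility estimand is declared for either.

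**Conclusion.** The inconsistency is real and follows from the text alone. SAP 5.3.1.2 says discontinuation is captured, yet a subject who stops early, has an exit MADRS on Day 33 or later and shows at least a 50% reduction counts as a Week 6 responder. Stoppers whose exit visit falls on Day 32 or earlier are handled as the estimand states, so the gap is confined to late exits.

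On the stated assumptions, about 1 to 10 of 280 subjects are affected, or 0.25 to 3.75 percentage points of the overall response rate. Even timing with every exit score obtained gives about 12 late exits, not all of them responders. These figures describe the overall rate, not a treatment difference. The change is worth making because following the plan as written contradicts its own estimand and the remedy is cheap.

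**What to change.** In SAP 5.3.1.2, replace the variable's missing-score rule with wording such as: subjects who discontinued study drug early, as recorded on the Trial Disposition for Double-blind Phase CRF page, are non-responders at Week 6 whether or not a MADRS falls in the Day 42 window; subjects with no Week 6 MADRS are also non-responders. Using recorded disposition leaves completers seen slightly early within the ±2-day window unaffected. Keep the observed-case analysis as planned. Applying the same rule to Week 6 remission (SAP 5.3.2.1) is optional, for consistency.

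The cost is one sentence and one programming flag from data already collected. Reported response rates may be slightly lower.

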#### 5.2.2. Primary Estimand

The primary estimand, the main clinical quantity of interest to be estimated in the study, is defined by the following 4 components:

**Population:** subjects with MDD who have had an inadequate response to current antidepressant therapy with an SSRI/SNRI, as defined through appropriate inclusion/exclusion criteria to reflect the targeted patient population;

Variable: change in MADRS total score from baseline to the end of Week 6 (see Section 5.2.1);

**Intervention Effect:** the effect of the initially randomized treatment together with the oral SSRI/SNRI antidepressant that would have been observed had all subjects remained on their treatment throughout the double-blind phase;

Summary Measure: the difference in variable means.

The primary analysis will be based on the full analysis set and the MADRS total scores collected during the double-blind phase.

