#### 5.2.3.2. MMRM Pairwise Comparisons

In conjunction with the MCP-Mod analysis, the pairwise comparison between JNJ-42847922 doses and placebo will also be performed using the appropriate contrasts directly from the MMRM analysis described in Section 5.2.3.1, using estimates at the end of Week 6. A 90% CI for the difference in LS Means and p-value will be calculated based on the contrast test statistic for each JNJ-42847922 dose level.

As a secondary analysis, age and gender will be added to the MMRM model described in Section 5.2.3.1 for the pairwise comparison between JNJ-42847922 doses and placebo.

As a sensitivity analysis, the change in MADRS total score from baseline to the end of Week 6 will be analyzed in an MMRM analysis with the exclusion of subjects with major protocol deviations that may affect efficacy (e.g., developed withdrawal criteria but not withdrawn, entered but did not satisfy criteria, received a disallowed concomitant treatment, received wrong treatment or incorrect dose and others that may affect efficacy).

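### The responder estimand is a difference in proportions, but the only planned comparison with a confidence interval is a ratio

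*SAP*

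**What the plan says.** SAP section 5.3.1.2 treats the proportion of MADRS responders at Week 6 as a utility estimand with four components. The variable is binary, and a subject without a Week 6 score counts as a non-responder. The summary measure is "the difference in response proportions".

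Section 5.3.1.3 describes the analysis. The descriptive part reads: "The number and percentage of subjects who achieve a response will be summarized at each time point during the double-blind phase by treatment group". The comparison between groups reads: "The point estimate and 2-sided 90% confidence interval will be provided for the relative response using a Mantel-Haenszel test", stratified by region and baseline insomnia status. The rest of that section covers cumulative response graphs and a Kaplan-Meier and log rank analysis of time to sustained response.

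On missing data, section 5.1.2 says that for the responder and remitter analyses "both observed case and imputed case where subjects with missing values will be imputed as non-responders/non-remitters will be presented".

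For the primary endpoint, the summary measure in section 5.2.2 is "the difference in variable means", and section 5.2.3.2 plans the matching estimate: "A 90% CI for the difference in LS Means and p-value will be calculated".

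**The concern.** An estimand's summary measure states the scale on which the treatment effect is to be estimated. Here the estimand asks for an absolute difference, and the planned stratified estimate and its precision come on a relative scale. Neither scale determines the other unless the placebo response rate is known.

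As written, the quantity the estimand names gets no adjusted estimate and no interval. The analyst must either report a scale the estimand does not name or add an analysis that was not pre-specified. The SAP does match scale to estimand for the primary endpoint, so the mismatch is specific to section 5.3.1. The SAP presents this estimand as combining efficacy and tolerability, and protocol section 1.2 says the trial's results will inform the choice of Phase 3 doses and endpoints. The absolute difference is therefore a number readers will look for.

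**Working it through.** **Step 1. Is relative response a ratio?** The SAP does not use the word ratio. However, section 5.3.2.2 applies the same Mantel-Haenszel method, with the same strata, to remission and calls the result a relative risk. No other reading of section 5.3.1.3 is reasonable.

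**Step 2. Is a difference with an interval planned elsewhere?** No.
- The other inferential item in section 5.3.1.3 is the stratified log rank test. It concerns time to sustained response, a different variable, and no interval is stated for it.
- Protocol section 11.3 plans only frequency distributions for responders.
- Neither document plans a difference in response rates with a confidence interval.

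**Step 3. Size.** The plan has no figure to reproduce: it gives no response rates and no power for this endpoint. Inputs:
- From the SAP (sections 1.2, 1.4 and 1.5): about 280 randomized, initial allocation 2:1:1, interim cutoff based on 160 subjects, allocation open to change afterwards, and a 10 mg arm that may be added.
- Assumed: placebo response 20%, 30% or 40%, with a ratio of 1.5.
- Assumed arm sizes, case A: 2:1:1 throughout, so 280 × 2/4 = 140 placebo and 280 × 1/4 = 70 per dose.
- Assumed arm sizes, case B: a dose added after the interim. Placebo has 160 × 2/4 = 80 before and 40 after, so 120; the added arm has 40. This ignores subjects randomized at the initial ratio while the interim was being prepared and reviewed.

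Formulas, without stratification, z = 1.645:
- SE(difference) = √[p0(1−p0)/n0 + p1(1−p1)/n1]
- SE(log ratio) = √[(1−p0)/(n0·p0) + (1−p1)/(n1·p1)]

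Worked case (20% vs 30%, 140/70): SE = √(0.16/140 + 0.21/70) = 0.0644. The 90% CI is 10 ± 1.645 × 6.44 points, or −0.6 to 20.6.

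| Placebo vs dose | Difference (points) | 90% CI, 140/70 | 90% CI, 120/40 | Ratio and 90% CI, 140/70 |
|---|---|---|---|---|
| 20% vs 30% | 10 | −0.6 to 20.6 | −3.3 to 23.3 | 1.5 (0.996 to 2.26) |
| 30% vs 45% | 15 | 3.3 to 26.7 | 0.3 to 29.7 | 1.5 (1.11 to 2.03) |
| 40% vs 60% | 20 | 8.2 to 31.8 | 5.3 to 34.7 | 1.5 (1.19 to 1.90) |

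The SEs of the difference are 0.0644, 0.0710 and 0.0717 at 140/70, and 0.0811, 0.0891 and 0.0894 at 120/40. One ratio goes with differences that double over this range, and the interval is about 21 to 29 points wide. In each row at 140/70 the ratio and difference intervals agree on whether the null value is excluded.

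**Step 4. Can subtraction replace a stratified difference?** A hypothetical worst case: placebo response is 40% in one region and 20% in the other, and the true gain is 15 points in both. The higher-response region supplies 60% of placebo subjects but 40% of an added arm.
- Active: 0.4 × 0.55 + 0.6 × 0.35 = 0.43
- Placebo: 0.6 × 0.40 + 0.4 × 0.20 = 0.32
- Crude difference: 0.43 − 0.32 = 11 points
- Mantel-Haenszel difference: a weighted average of 15 and 15, so 15 points
- Mantel-Haenszel ratio: 1.52

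The planned ratio would be adjusted for the regional imbalance; the subtraction would not.

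**The case against.** The strongest reply is that the named quantity will in effect be reported. The tables give responders by arm, with missing counted as non-response, so the crude difference and a simple interval follow from the counts. Section 5.3.1.2 does not require stratum adjustment. This is a secondary endpoint with no Type I error control, in a trial the protocol (section 11.8) describes as not confirmatory, and the protocol itself plans only frequencies. If changing one phrase in the estimand cures the problem, it looks like a wording inconsistency.

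Much of this stands as a limit on importance. Because the placebo percentage is shown, a reader will know which of the 10, 15 or 20 point cases applies. The interval widths reflect sample size and are not caused by the mismatch; they show how much uncertainty would go unreported on the estimand's scale.

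The 11 against 15 example is also demanding. Randomization is stratified by region, so arms recruited concurrently should have similar regional mixes. With 120 placebo and 40 added-arm subjects, post-interim placebo would resemble the added arm (16 of 40 from the higher-response region). Reaching 60% overall (72 of 120) then requires 72 − 16 = 56 of 80, or 70%, before the interim. Regional recruitment must fall from 70% to 40%, the regions must differ twofold in placebo response, and a dose must be added. It cannot arise for a dose whose ratio to placebo never changes.

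What does not stand is the conclusion that nothing is missing. A crude interval that readers construct themselves is not a pre-specified analysis, and the SAP evidently considers stratification appropriate because it applies it to the ratio.

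**Conclusion.** The concern holds. The estimand's summary measure is a difference, the only between-group response estimate planned with an interval is a ratio, and nothing else in the protocol or SAP fills the gap. This conclusion rests on the text and needs no assumption.

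The size does need assumptions. For placebo response of 20% to 40% and a ratio of 1.5, the absolute difference runs from 10 to 20 points, and its unplanned 90% interval is about 21 to 29 points wide. Subtracting crude percentages could be off by 4 points (11 instead of 15) in a worst case that needs an added arm and a marked shift in regional recruitment. For doses carried throughout at a constant ratio to placebo, crude and stratified differences should be close.

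The consequence is moderate: the reporting of one uncontrolled secondary endpoint. The primary MADRS analysis is unaffected, and whether the null is rejected need not change. It should still be corrected, because the estimand and its analysis disagree and the remedy is nearly free.

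**What to change.** In SAP section 5.3.1.3, add for each dose against placebo the Mantel-Haenszel stratum-weighted difference in response rates with a 2-sided 90% confidence interval. Use the strata already specified (region and baseline insomnia status) and count missing Week 6 scores as non-response, as the estimand requires. Keep the relative response alongside it. The cost is one SAP sentence and one extra estimate per dose in the responder table.

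Alternatively, if the ratio is the intended measure, change the summary measure in section 5.3.1.2 to the ratio of response proportions. That is a one-phrase edit with no change to the analysis. Neither option needs new data or affects trial conduct.
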